10.2.2 Exposure-adjusted incidence rate and exposure-adjusted event rate

The time at risk (in days) at AE onset is the same as the time since first bimekizumab dose as described in [Section 10.2.1](#).

Total time at risk (as defined in [Section 10.1](#)) and time at risk at AE onset will be divided by 365.25 to give years at risk.

EAIR and EAER will be calculated separately for tables including all events in AS0008 and AS0009 combined, and for tables including events with onset in AS0009 only. The former tables will use time at risk relative to the start date of bimekizumab 160mg or 320mg (for the ‘BKZ 160mg’ and ‘BKZ 320mg’ columns) and time at risk relative to the date of the first dose of bimekizumab (for the ‘BKZ Total’ column). The latter table will use time at risk relative to the start date of study medication in AS0009.

The EAIR is defined as the number of subjects with a specific AE adjusted for the exposure and will be scaled to 100 patient-years:

$$\frac{EAIR = 100 * n_{AE}}{\sum_{i=1}^{n_{AE}} T_{Exp,i} + \sum_{j=1}^{n_{noAE}} T_{Risk,j}} \quad (20)$$

Where n_{AE} is the number of subjects with the AE, $T_{Exp,i}$ is a subject’s time at risk at AE onset in years (equation [15] in years) and $T_{Risk,j}$ is the time at risk in years for subjects who did not experience the AE of interest.

If a subject has multiple events at the level of coding evaluated, the time at risk at AE onset is calculated to the first occurrence of the AE.

Exact Poisson 95% CIs for incidence rates are calculated using the relationship between the Poisson and the chi-square distribution (Ulm, 1990; Fay and Feuer, 1997):

$$LCL = \frac{\chi^2_{2n,\frac{\alpha}{2}}}{2} \quad (21)$$

$$UCL = \frac{\chi^2_{2(n+1),1-\frac{\alpha}{2}}}{2} \quad (22)$$

$$CI_{Lower} = 100 * \frac{LCL}{\sum_{i=1}^{n_{AE}} T_{Exp,i} + \sum_{j=1}^{n_{noAE}} T_{Risk,j}} \quad (23)$$

$$CI_{Upper} = 100 * UCL \frac{UCL}{\sum_{i=1}^{n_{AE}} T_{Exp,i} + \sum_{j=1}^{n_{noAE}} T_{Risk,j}} \quad (24)$$

where n_{AE} is the number of subjects with the AE and is the basis for the number of the degrees of freedom for the chi-square quantile for the upper tail probability χ^2 , $T_{Exp,i}$ is a subject's time at risk at AE onset in years, n_{noAE} the number of subjects without the specific AE and $T_{Risk,j}$ the total time at risk for subjects who did not experience the AE.

The EAER is defined as the number of AEs reported up to 140 days after last dose, including repeat occurrences in individual subjects, and adjusted for exposure, and will be scaled to 100 subject-years:

$$\frac{EAER = 100 * N_{AE}}{\sum_{j=1}^{n_{All}} T_{Risk,j}} \quad (25)$$

where N_{AE} is the total number of AEs, $T_{Risk,j}$ is a subject's total time at risk in years and n_{All} the number of subjects.

No CI will be computed for EAER.

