8.5 Impact of COVID-19

Additional sensitivity analyses as a result of the global COVID-19 pandemic are not anticipated as the onset of the pandemic was subsequent to all subjects completing Week 48 and therefore there is no impact on the analysis of the secondary efficacy endpoint.

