10.2.1 Adverse event duration and time since first/last dose

Missing start or end dates will be imputed as described in [Section 4.2.2](#) prior to any calculation described in this section.

The duration of each AE will be calculated as follows:

$$\text{Duration (days)} = \text{date of outcome} - \text{date of onset} + 1 \quad (15)$$

The time since first bimekizumab dose for each TEAE will be calculated three times for each of the reference dates below:

- Relative to the date of first administration of bimekizumab in AS0008.
- Relative to the date of the first dose of bimekizumab 160mg, only for AEs with onset during treatment with bimekizumab 160mg OR
- Relative to the date of the first dose of bimekizumab 320mg, only for AEs with onset during treatment with bimekizumab 320mg.
 - For these criteria during treatment refers to TEAEs with onset up to 140 days after the last dose on that treatment.
- Relative to the start date of study medication in AS0009.

Time since first dose will be calculated as follows for AEs occurring on or after the reference date (as defined above):

$$\begin{aligned} \text{Time since first BKZ dose (days)} \\ = \text{Date of AE onset} - \text{Reference date} + 1 \end{aligned} \quad (16)$$

The time since most recent bimekizumab dose for each TEAE will be calculated as follows for AEs occurring on or after the reference date (as defined above):

$$\begin{aligned} \text{Time since most recent BKZ dose (days)} \\ = \text{Date of AE onset} \\ - \text{Date of most recent dose prior to AE} + 1 \end{aligned} \quad (17)$$

For any AE occurring on the same day as a given dosing occasion the most recent dose will be considered to be the dose given on the same day i.e., time since most recent dose would be equal to 1 for all such AEs.

For AEs occurring prior to the reference date (as defined above) the time since dosing will be calculated as follows for first/most recent BKZ dose:

$$\text{Time since BKZ dose (days)} = \text{Date of AE onset} - \text{Reference date} \quad (18)$$

Days on treatment at AE onset will be calculated three times using the same three reference dates as for time since first dose. Days on treatment at AE onset will be calculated as:

$$\begin{aligned} \text{Days on treatment at AE onset} \\ = \text{Date of last or latest dose prior to AE onset} \\ - \text{Reference date} + 1 \end{aligned} \quad (19)$$

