10.2.4 Impact of COVID-19

In order to assess the impact of the COVID-19 global pandemic on the primary safety endpoint of incidence of TEAEs and serious TEAEs, additional listings and summaries will be presented.

For reporting purposes AEs will be assigned to ‘Prior to COVID-19 pandemic’, ‘During the COVID-19 pandemic’ or ‘Post the COVID-19 pandemic’ based on the following:

- If the date of AE onset (based on imputed start date) is prior to 11 March 2020 the AE will be assigned as ‘Prior to COVID-19 pandemic’
- If the date of AE onset (based on imputed start date) is on or after 11 March 2020 the AE will be assigned as ‘During the COVID-19 pandemic’
 - The date of 11 March 2020 is chosen as the date the World Health Organization declared COVID-19 as a pandemic.

- If the date of AE onset (based on imputed start date) is after the date on which the World Health Organization declares the end of the COVID-19 pandemic the AE will be assigned as ‘Post the COVID-19 pandemic’
 - If the date of the end of the COVID-19 pandemic is on or after the date of last subject, last visit, the ‘Post the COVID-19 pandemic’ phase will not apply.

The following categories of TEAE will be summarized by MedDRA SOC, HLT and PT, including EAIR and EAER:

- All TEAEs by time of onset relative to COVID-19 pandemic (‘Prior to COVID-19 pandemic’, ‘During the COVID-19 pandemic’ and ‘Post the COVID-19 pandemic’)
- All serious TEAEs by time of onset relative to COVID-19 pandemic (‘Prior to COVID-19 pandemic’, ‘During the COVID-19 pandemic’ and ‘Post the COVID-19 pandemic’)
- All COVID-19 related TEAEs by treatment at completion of AS0008 and overall
 - COVID-19 related TEAEs will be identified based on the verbatim term including the text string ‘COVID’. These will include confirmed or suspected COVID-19 infections.

TEAEs leading to study discontinuation and/or permanent withdrawal of study medication will be summarized by MedDRA SOC, HLT, and PT, and by time of onset relative to COVID-19 pandemic (‘Prior to COVID-19 pandemic’, ‘During the COVID-19 pandemic’ and ‘Post the COVID-19 pandemic’).

A separate listing of all COVID-19 related AEs will be presented, where COVID-related AEs are identified as described above. In addition, the time of onset of each AE relative to the COVID-19 pandemic will be flagged in all AE listings.

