For all listings and summaries described above the ‘Post the COVID-19 pandemic’ phase will be omitted if the date of the end of the COVID-19 pandemic is on or after the date of last subject, last visit.

For the purpose of calculating EAIR and EAER prior to, during, and post the COVID-19 pandemic the rules in [Table 10-5](#) will be applied in the calculation of exposure time at risk. An individual subject may therefore be counted in the denominator for all applicable periods (‘Prior to COVID-19 pandemic’, ‘During the COVID-19 pandemic’ and ‘Post the COVID-19 pandemic’), dependent on whether the subject is still considered at risk at the time of the start date for each successive period. The time at risk will be calculated separately for each period in which the subject is counted. Subjects who are no longer in the exposure time at risk period ([Table 10-2](#)) on the start date of a specific COVID-19 reporting period will not be counted in the denominator for that period ie, a subject who has withdrawn from the study prior to 11 March 2020 and is no longer at risk will not be included in the denominator for the ‘During the COVID-19 pandemic’ or the ‘Post the COVID-19’ pandemic periods.

Table 10-5: Calculation of exposure time at risk in relation to COVID-19

Study Period	Start Date	End Date	Duration of Exposure

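### COVID-period AE tables (SAP 10.2.4): time at risk restarts at the period start for subjects without the event, but time to onset still runs from the first AS0009 dose, so the During and Post EAIRs mix two clocks

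*SAP*

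**What the plan says.** **The rate.** Equation 20 in SAP 10.2.2 divides the number of subjects with the event by the sum of two quantities: T_Exp for subjects with the event and T_Risk for those without. On T_Exp, 10.2.2 states: "The time at risk (in days) at AE onset is the same as the time since first bimekizumab dose". For tables limited to AS0009 events it adds: "The latter table will use time at risk relative to the start date of study medication in AS0009". The reference dates in 10.2.1 are all dosing dates; the one that applies here is "Relative to the start date of study medication in AS0009". None is the start of a pandemic period.

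**The COVID tables.** SAP 10.2.4 asks for EAIR and EAER in "All TEAEs by time of onset relative to COVID-19 pandemic", and likewise for serious TEAEs. It applies Table 10-5 to the exposure time at risk, which is the Table 10-2 quantity, and says: "The time at risk will be calculated separately for each period in which the subject is counted". Table 10-5 starts *Prior* at the first AS0009 dose, *During* on 11MAR2020 and *Post* on the day after the pandemic ends. It has no rule that stops the clock at AE onset. The *Post* phase is dropped if the pandemic ends on or after the last subject's last visit.

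**Timing.** SAP 8.5 states that "the onset of the pandemic was subsequent to all subjects completing Week 48".

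**The concern.** Both terms of the EAIR denominator should measure person-time inside the same window. In *During* and *Post*, a subject without the event contributes only time inside the window. A subject with the event contributes everything since the first AS0009 dose, most of which may lie in an earlier column.

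These tables are meant to show whether the pandemic affected TEAEs and serious TEAEs. *Prior* is internally consistent, because both clocks start at the first AS0009 dose. An error confined to the later columns distorts exactly the comparison the tables exist for: it could create an apparent fall in incidence or hide a rise. Equations 23 and 24 use the same denominator, so the confidence limits are scaled by the same factor.

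**Working it through.** The plan states no COVID-period EAIR, so there is no figure to reproduce. The check evaluates equation 20 under each reading.

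**Size of the gap, d** (first AS0009 dose to 11 March 2020)
- Minimum: all subjects had completed Week 48 (SAP 8.5), so 48 × 7 / 365.25 = 0.92 year. With the 7-day visit window it could be 329 / 365.25 = 0.90.
- Maximum: 15 May 2017 (final protocol date, SAP 1) to 11 March 2020 is 1031 days, or 2.82 years, assuming no dose before the protocol was final.
- *Post*: d also includes the whole pandemic period.

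**One subject** (assumed dates). First dose 1 June 2018, onset 11 June 2020. T_Exp under 10.2.2 is 742 days. In-period time is 93 days.

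**Any TEAE in *During*, first occurrence counted within the period.** Assumed: 240 at risk; 60% (144) with an event at a mean of 0.6 year into the period; the other 96 followed for 1.8 years.
- Aligned clocks: 144 × 0.6 + 96 × 1.8 = 86.4 + 172.8 = 259.2 PY; 144 / 259.2 = 55.6 per 100 PY.
- As written, d = 0.92: 259.2 + 144 × 0.92 = 391.7 PY; 36.8 per 100 PY (−34%).
- As written, d = 1.5: 259.2 + 216 = 475.2 PY; 30.3 per 100 PY (−45%).

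The last denominator shows that something is wrong. If all 240 were followed for 1.8 years, total person-time at risk (the EAER denominator, equation 25) is 432 PY. Time to first event cannot exceed that.

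**Serious TEAEs.** Assumed: 6% of 240 (14.4 expected) with onset at 0.9 year; the other 225.6 followed for 1.5 years.
- Aligned: 12.96 + 338.4 = 351.4 PY; 4.10 per 100 PY.
- As written: 364.6 PY at d = 0.92 (−3.6%) and 373.0 PY at d = 1.5 (−5.8%).

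**General form.** With a constant in-period rate λ per year and a common gap d, the expression tends to λ / (1 + λd), whatever the period length. For d from 0.92 to 2.82:

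| True rate per 100 PY | Relative error |
|---|---|
| 1 | −0.9% to −2.7% |
| 5 | −4% to −12% |
| 50 | −32% to −59% |

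**First occurrence counted within the study.** T_Exp can then end before the period opens. Assume a mean T_Exp of 0.5 year to an earlier first event and keep the other any-TEAE inputs: 144 / (144 × 0.5 + 172.8) = 144 / 244.8 = 58.8 per 100 PY, against 55.6. The rate is still wrong, here slightly high.

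**The case against.** The strongest reply is that 10.2.4 already covers this. It introduces its rules as serving both EAIR and EAER, calls for time at risk to be computed per period, and is the more specific section. A programmer could reasonably restart the onset clock as well. That stands as a statement about intent, and the text does not show what was programmed.

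It does not repair the rule. Table 10-5 contains no onset rule, so applying it as written to subjects with events gives them the full period: 144 / 432 = 33.3 per 100 PY in the any-TEAE example, again too low. The aligned rate needs an instruction that the SAP does not contain.

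A second reply concerns direction. Section 10.2.2 runs T_Exp to the first occurrence without saying whether that is first in the study or first in the period. This stands: the downward direction is conditional on the within-period reading, and is least secure for any TEAE, where earlier events are likeliest.

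A third reply concerns importance. These are supplementary descriptive tables added because of the pandemic (SAP 3.10.1). EAER uses T_Risk only and appears in the same tables, so a correctly clocked rate sits beside the faulty one. That also stands, and it limits the severity.

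**Conclusion.** The rule is wrong as written for the *During* EAIR, and for the *Post* EAIR if that column is produced. Counting first occurrence within the period, the error is downward. It is substantial for any TEAE and common SOC rows (about −34% or more in the example) and a few percent for serious or rare events. Only the 48-week minimum gap and the calendar dates come from the documents; event proportions, onset times and follow-up are assumed.

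A reader might infer more than this supports:
- That the trial's main safety results are biased. The main AS0009 TEAE tables use one clock throughout; they, the *Prior* column and all EAERs are unaffected.
- That 11 March 2020 is the restart date for both later columns. It applies to *During* only; *Post* restarts after the pandemic ends, which widens the mismatch.
- That the reported rates are certainly too low. That depends on the first-occurrence rule and on the programming, and the documents settle neither.

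Severity: moderate.

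**What to change.** Add to SAP 10.2.4: for each COVID period, T_Exp = date of first onset within that period − period start date + 1. The period start is the first AS0009 dose (*Prior*), 11MAR2020 (*During*) or the day after the end of the pandemic (*Post*). T_Risk for subjects without the event in that period stays as in Table 10-5.

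In 10.2.2, correct the cross-reference for T_Exp from equation 15, which is AE duration, to equation 16, which is time since first dose.

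A simple programming check follows: in any row and column, the EAIR person-time must not exceed the EAER person-time.

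Cost: one sentence, one corrected reference and a small programming change. No new data are needed.

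### SAP 10.2.2 cites the AE-duration equation for time at risk in the EAIR formula and misnames the chi-square tail; both need a small correction

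*SAP*

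**What the plan says.** SAP 10.2.2 opens with a definition in words: "The time at risk (in days) at AE onset is the same as the time since first bimekizumab dose as described in" SAP 10.2.1. There, time since first dose is equation 16: onset date minus reference date plus 1. Section 10.2.2 then names the reference date for each type of table. For repeated events it adds that "the time at risk at AE onset is calculated to the first occurrence of the AE".

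The legend under the EAIR formula (equation 20) gives the same term, T_Exp, as "time at risk at AE onset in years (equation [15] in years". Equation 15 belongs to another quantity. SAP 10.2.1 introduces it with "The duration of each AE will be calculated as follows", and it is outcome date minus onset date plus 1.

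For the interval, the SAP names the exact Poisson method through the chi-square relationship. Equation 21 takes the quantile with subscript alpha/2 and 2n degrees of freedom for LCL. Equation 22 takes subscript 1 - alpha/2 and 2(n+1) degrees of freedom for UCL. The legend below them refers to "the chi-square quantile for the upper tail probability". In the text as extracted from the PDF, equation 24 begins "CI_{Upper} = 100 * UCL" and then has UCL again in the numerator of the fraction. Equation 23, otherwise parallel, has LCL once.

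**The concern.** One section gives two meanings for the person-time contributed by subjects who had the event: time from first dose to onset (opening sentence) and length of the event (equation number in the legend). These are unrelated quantities.

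The rate reaches widely. EAIR accompanies the tables of all TEAEs and serious TEAEs (SAP 10.2), whose incidences are the primary safety variables (SAP 2.2.1.1). It is also in the safety-topic tables (10.2.3) and the tables by COVID-19 period (10.2.4). A programmer who works from the formula and its legend could take the cited equation at face value. The denominator would then lose most of the time that affected subjects spent at risk before a short event. An event with a completely unknown stop date would have no T_Exp at all, because SAP 4.2.2 leaves such dates unimputed (partial stop dates are imputed).

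The tail wording is a second conflict between legend and formula: applied to the printed subscripts, it puts the lower limit above the upper.

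**Working it through.** The documents state no EAIR or confidence limit to reproduce, so the check evaluates the formulas under stated assumptions.

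**1. Which equation is meant.** The opening sentence, the reference date per table and the first-occurrence rule all fit equation 16. A duration has no first-dose reference date and does not run to a first occurrence.

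**2. Size if equation 15 were used.** EAIR = 100·n / (n·T + (N − n)·R), where T is the mean T_Exp in years and R the mean time at risk of unaffected subjects. Assumptions, not in the documents: N = 255, mean onset 0.6 years, R = 3.0 years, event duration 14 days (14/365.25 = 0.0383 years).

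- Any TEAE, n = 230. Equation 16: 23,000 / (138 + 75) = 108.0 per 100 patient-years. Equation 15: 23,000 / (8.8 + 75) = 274. Ratio 2.5.
- Same case, other durations. 7 days: 23,000 / (4.4 + 75) = 290, ratio 2.7. 60 days: 23,000 / (37.8 + 75) = 204, ratio 1.9.
- A term in n = 100. Equation 16: 10,000 / (60 + 465) = 19.0. Equation 15: 10,000 / (3.8 + 465) = 21.3. Ratio 1.12.
- A term in n = 5. Equation 16: 500 / (3 + 750) = 0.664. Equation 15: 500 / (0.19 + 750) = 0.666. Ratio 1.00.

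A second set of assumptions uses the planned maximum of 285 subjects, all with the longest time at risk, (204·7 + 140 + 1)/365.25 = 4.30 years. Onset is exponential and mean event duration runs from 90 down to 7 days:

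| Subjects with event | EAIR by eq. 15 / EAIR by eq. 16 |
|---|---|
| about 1% | 1.00 |
| 4% | 1.02 |
| 19% | 1.10 to 1.11 |
| 35% | 1.21 to 1.25 |
| 88% | 2.5 to 3.4 |
| 99% | 3.3 to 12.5 |

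The inflation arises because these durations are shorter than the mean time to onset. Events that outlast their time to onset would push the rate the other way.

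**3. Tail of the chi-square quantile.** For n = 10 and alpha = 0.05, lower-tail quantiles in equations 21 and 22 give LCL 4.795 and UCL 18.390. Each leaves a Poisson tail probability of 0.025, so these are the exact limits. With upper-tail quantiles the same subscripts give LCL 17.09 and UCL 5.49, which is out of order.

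**4. Equation 24.** For n = 5 in an assumed 850 patient-years, LCL = 1.623 and UCL = 11.668. The limits are 100·1.623/850 = 0.19 and 100·11.668/850 = 1.37. With UCL twice, the upper limit would be 100·11.668²/850 = 16.0.

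**The case against.** The best defence is that the section already settles the meaning. It defines the term correctly in words, fixes its reference dates, says that it runs to first occurrence, and repeats the name without an equation number in the second legend. On this view the 15 is a stale cross-reference. SAP 13.2.2 records that Amendment 2 added the fold-change calculation for antibody titers, now equation 14. One inserted equation would have moved time since first dose from 15 to 16. That origin is an inference, but a plausible one. The defence largely stands: a careful programmer would probably use the right quantity. It does not remove the conflict, because the equation number sits in the legend of the formula that will be coded.

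Three stronger readings are tempting and are not supported:

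- A reader might infer that the reported rates will be badly wrong. That requires following one bracketed number against all the surrounding text, and even then only very common events move much.
- A reader might infer that the confidence-limit formulas are wrong as a set. Equations 21 to 23 are correct with lower-tail quantiles; only the tail wording is at fault.
- A reader might count the doubled UCL in equation 24 as an error of the plan. Equations 8, 11, 20 and 25 also came through PDF extraction garbled, with the left-hand side inside the fraction, so this may be an artefact. The named method and equation 23 show the intent.

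EAIR is also not the only presentation of the primary variable. SAP 10.2 presents numbers and percentages of subjects and numbers of events, which do not use T_Exp. EAER uses only total time at risk.

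**Conclusion.** Two statements in SAP 10.2.2 are wrong as written. The legend of equation 20 cites AE duration where the section's own definition requires time since first dose, and the tail wording does not fit the subscripts of equations 21 and 22. Both are certain from the text. The consequence is conditional: only literal use of the citation would inflate the EAIR, about 2.5-fold for any TEAE under the illustrative inputs (1.9- to 2.7-fold for durations of 60 to 7 days), with a negligible effect for rare terms. These sizes rest on assumed onset times, follow-up and durations that the documents do not give. The tail wording, if applied, would give visibly reversed limits and so would probably be caught. This is a correction to an operative formula that the surrounding text already largely resolves. It need not hold up the plan.

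**What to change.** In SAP 10.2.2:

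1. In the legend of equation 20, cite equation 16 instead of equation 15.
2. In the legend of the confidence limits, describe the chi-square subscripts as lower-tail (cumulative) probabilities.
3. Check equation 24 in the source document. If UCL does appear twice there, write the upper limit as 100 times UCL divided by the total time at risk, parallel to equation 23.

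The cost is two wording changes and one check in a single section. No new data, analysis or table is needed. If the tables are already programmed, confirm that the code takes T_Exp from first dose to first onset and uses cumulative quantiles.
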